6.1.8. Data Adjustments/Handling/Conventions

All collected data will be presented in listings. Data not subject to analysis according to this plan will not appear in any tables or graphs but will be included only in the data listings.

All p-values will be displayed in 4 decimals and rounded using standard scientific notation (eg, 0.XXXX). If a p-value less than 0.0001 occurs, it will be shown in tables as <0.0001.

All AEs and medical histories will be coded using the Medical Dictionary for Regulatory Activities (MedDRA) version 20.1 thesaurus. Prior and concomitant medications will be coded using the World Health Organization-Drug Dictionary Enhanced (WHO-DDE) version September 2017.

A treatment related AE is any AE with a relationship to the study drug of possibly, probably, or likely related.

If partial dates occur, the convention for replacing missing dates for the purpose of statistical analysis is as follows:

For partial AE and medication start dates:

- if just day is missing then the day assigned is the first day of the month or the date of first dose (if in the same month), whichever is later;

- if just month is missing then the month assigned is the month of the first dose, unless that results in a date prior to the first dose in which case the month after the first dose is used; and
- if both month and day are missing then the month assigned is the month of the first dose and the day assigned is the first dose day.

For partial AE and medication end dates:

- if just day is missing then the day assigned is the day of the last date on study (ie, date of last contact if subject lost to follow-up or date of completion / early termination) if month and year do match the month and year of the last date of the study, or the last day of the month otherwise;
- if just month is missing then the month assigned is the month of the last date on study, unless that results in a date after the last date on study, in which case the month before the last date on study is used; and
- if both month and day are missing then the month assigned is the month of the last date on study and the day assigned is the day of last date on study, unless that results in a date after the last date on study, in which case the first day of the month is assigned.

If partial times occur, the convention is as follows:

- if the missing time occurs on the day of the first dose and both the hour and minute are missing then the time assigned is the time of the first dose, otherwise if both the hour and minute are missing and the date is not the date of first dose the time assigned is 12:00;
- if the date is the same as the date of the first dose and
 - only hour is missing the hour assigned is 12 or the hour of first dose, whichever is later;
 - only the minute is missing the minute assigned is 30 or the minute of first dose, whichever is later;
- Otherwise if the date is not the same as the date of first dose, the hour assigned is 12 if the hour is missing and the minute assigned is 30 if the minute is missing.

The time imputation only applies to Cohort 1. If a Cohort 2 time is missing, set to 12:00; if time is incomplete, set to 12 (hour) or 00 (minute).

7. Study Subjects and Demographics

Individual subject listings will be prepared for all study subjects and demographics data.

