9.3 Safety Evaluation

The following analyses will be performed; however, no formal inferential statistics will be performed on safety assessments.

Descriptive statistics will be calculated for quantitative safety data and frequency counts will be compiled for classification of qualitative safety data.

Adverse Events:

The assessment of safety will be based mainly on the frequency and percent of subjects who reported treatment-emergent AEs.

Adverse events will be coded using the Medical Dictionary for Drug Regulatory Activities (MedDRA) Version 18.1 or higher. Treatment emergent adverse events (i.e. events with onset dates on or after the start of study drug or with missing onset dates) will be summarized by presenting for each treatment group, the number and percentage of subjects having any AE, having an AE in an individual body system, and having an AE in an individual preferred term. Any other information collected (e.g. severity or relatedness to study medication) will be listed as appropriate.

Application Site Reaction

The numeric application site reaction scores will be summarized individually by using number and percentage of subjects by visit.

Medical History and Physical Examinations:

Medical history for all subjects will be presented in a by-subject listing.

Physical examination findings for all subjects will be presented in a by-subject listing. Changes in physical examinations will be described in the text of the final report.

Clinical Laboratory Results, Electrocardiograms and Vital Signs Measurements:12

All clinical laboratory results, 12-lead ECGs and vital signs measurements and their change from baseline (pre-dose), will be summarized along with time point of collection.

A shift table describing out-of-normal range shifts will be provided for clinical laboratory results.

Prior and Concomitant Medications:

Prior and concomitant medication information for all randomized subjects will be presented in a by-subject listing. Summary tables will be presented by World Health Organization-Anatomical Therapeutic Chemical Classification System (WHO-ATC) therapeutic category and product.

Quick Inventory of Depressive Symptomatology-Self-Report (QIDS-SR):

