9.1. Adverse Events

An event that is temporally associated with administration of study product is defined as a treatment emergent adverse event (TEAE). Events meeting this definition will be those with a start date during or after administration of the first dose of study drug through the telephone follow-up in each cohort. For AEs occurring on the date of the first dose of study drug, if the time of onset is missing, the AE will be assumed to be treatment emergent.

The causal relationship of the AE to the study drug is determined by the investigator as Unrelated, Unlikely Related, Possibly Related, Probably Related, and Likely Related. These can be mapped to Unrelated (*Unrelated* and *Unlikely Related*) and Related (*Possibly Related*, *Probably Related*, and *Likely Related*).

Adverse event severity grades are reported on a 5-point scale of Grade 1 (*Mild*), Grade 2 (*Moderate*), Grade 3 (*Severe*), Grade 4 (*Life-threatening consequences*), or Grade 5 (*Death related to AE*).

An AE summary table will be presented for the following:

AD-ST-33.04 Effective date: 30-Jun-2017

- All TEAEs
- TEAEs by maximum severity
- Treatment-related TEAE
- TEAEs leading to discontinuation of study drug
- Serious AEs (SAEs)
- Deaths

Summaries of incidence rates (frequencies and percentages) of individual TEAEs by MedDRA (v20.1) system organ class (SOC) and preferred term (PT). Such summaries will be displayed for all TEAEs, TEAEs by maximum severity, and treatment-related. Analysis of TEAEs will be performed by treatment within cohort.

Each subject will be counted only once within each summation level (SOC and preferred term). If a subject experiences more than 1 TEAE within each summation level only, the TEAE with the strongest relationship or the maximum severity, as appropriate, will be included in the summaries of relationship and severity.

Incidence will be presented by descending frequency of SOC and PT within SOC, and then alphabetically within PT where the incidence is the same; this is based on overall subjects.

Missing and partially missing AE start and/or stop dates will be imputed, for the purpose of statistical analysis, according to the specifications described in [Section 6.1.8](#).

In the AE data listings, all AEs will be displayed. AEs that are treatment emergent will be flagged.

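### The missing-month rules in SAP 6.1.8 do not check the recorded year, so for a subject followed across New Year an imputed start or end can fall about 11 months outside participation

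*SAP*

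**What the plan says.** SAP 6.1.8 gives separate conventions for start and end dates of adverse events and medications.

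- **Start, month and day missing:** "if both month and day are missing then the month assigned is the month of the first dose"; the day is likewise that of the first dose. No guard is attached.
- **Start, only month missing:** the first-dose month, with this guard: "unless that results in a date prior to the first dose in which case the month after the first dose is used".
- **End, month and day missing:** "the month assigned is the month of the last date on study and the day assigned is the day of last date on study", with the first of the month as fallback if that date is later than the last date on study.
- **End, only month missing:** the month of the last date on study, or the month before it if the result would be too late.

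All four supply a month, or a month and day, and leave the recorded year as it stands. By contrast, the end-date rule for a missing day alone does compare both month and year with the last date on study.

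SAP 9.1 carries these dates into the analysis: "Missing and partially missing AE start and/or stop dates will be imputed, for the purpose of statistical analysis". The same section limits TEAEs to events "with a start date during or after administration of the first dose of study drug through the telephone follow-up in each cohort". SAP 6.1.7 instead defines a TEAE as any onset after first dose, with no closing date. Protocol 9.3 also has no closing date and describes TEAEs as "events with onset dates on or after the start of study drug or with missing onset dates". SAP 9.7 treats a medication as concomitant if it continues or starts after first dose, up to the follow-up visit.

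**The concern.** A month taken from a reference date makes sense only if the recorded year is the year of that date. When a subject is dosed in December and followed into January, the first-dose month belongs to the old year and the last-contact month to the new one. Putting December on a new-year start, or January on an old-year end, moves the date by most of a year and out of the subject's participation. The guards do not prevent this: the start guard looks only for dates that are too early, and the end guard only for dates that are too late.

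Two outputs depend on the result: the TEAE tables, where the answer turns on which SAP definition is programmed, and the concomitant medication table, where SAP 9.7 is the only definition.

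**Working it through.** The documents state no figure for this point. The check applies the SAP 6.1.8 rules literally.

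**Inputs**

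- Cohort 2 call on Day 35, within 1 day (SAP Table 2). With Day 1 as first dose, call = first dose + 34 days.
- Cohort 1 call on Day 8 (SAP Table 1), so first dose + 7 days; 1 day either way is also tried.
- First dose 12-Dec-2017: an assumption. The Cohort 2 call is then 15-Jan-2018, also taken as the last date on study.

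**1. Records run through the rules (Cohort 2)**

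| Recorded | Imputed | Position |
|---|---|---|
| Start UNK-UNK-2018 | 12-Dec-2018 | 331 days after the call |
| Start 05-UNK-2018 | 05-Dec-2018 | 324 days after the call |
| End UNK-UNK-2017 | 15-Jan-2017 | 331 days before first dose |
| End 20-UNK-2017 | 20-Jan-2017 | 326 days before first dose |

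Within participation, a 2018 start could only lie between 1 and 15 January 2018. No guard acts: neither start is before first dose, and neither end is after the last date on study.

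**2. General size of the shift**

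With month and day missing, gap after the call = 365 − (days from first dose to call).

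- Cohort 2: 365 − 34 = 331 days; 330 to 332 with the 1-day window (10.8 to 10.9 months).
- Cohort 1: 365 − 7 = 358 days; 357 to 359 with 1 day either way (11.7 to 11.8 months).

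With only the month missing, over all first-dose dates whose call falls in the new year, the gap is 300 to 334 days in Cohort 2 and 327 to 334 days in Cohort 1.

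**3. Who can be affected**

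For a call exactly on schedule to fall in 2018, first dose must lie between 28 November and 31 December 2017 (Cohort 2) or between 25 and 31 December 2017 (Cohort 1).

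**4. Classification of the imputed dates**

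| Definition | Record | Result |
|---|---|---|
| SAP 9.1 | AE onset 12-Dec-2018 | After the call: not a TEAE |
| SAP 6.1.7 | AE onset 12-Dec-2018 | After first dose: TEAE |
| Protocol 9.3 | AE onset 12-Dec-2018 | After start of study drug: TEAE |
| SAP 9.7 | Medication start 12-Dec-2018 | After follow-up: not concomitant; not before first dose: not prior |
| SAP 9.7 | Medication begun before first dose, end imputed 15-Jan-2017 | Appears stopped before dosing: not concomitant |

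**5. Effect per record**

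Planned Cohort 2 arm size is 84/3 = 28. One subject is 1/28 = 3.6 percentage points of incidence.

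**6. Control within one year**

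With first dose 15-Feb-2018 (call 21-Mar-2018), starts UNK-UNK-2018, 03-UNK-2018 and 20-UNK-2018 become 15-Feb, 03-Mar and 20-Feb-2018. All lie inside the study, so the fault is confined to the year boundary.

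**The case against.** The strongest objection concerns the TEAE consequence. A reader might infer that the affected event is simply lost from the treatment-emergent tables. The documents do not support that: only the SAP 9.1 window excludes it, while SAP 6.1.7 and Protocol 9.3 still count it. This stands. What remains is that two SAP sections give opposite answers for one record. Nor does the SAP rule directly contradict Protocol 9.3, whose clause on missing onset dates does not mention partial ones.

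The second objection is rarity. Cohort 2 has weekly visits and a call, a daily diary reviewed by staff, onset date and time recorded for each event, and a 100% quality control check before lock (Protocol 8.11.3, 8.16 and 9.7). A known year with an unknown month should be unusual for an on-treatment event. This also stands. The protocol dates (17 October and 06 December 2017) and SAP date (06 May 2018) make a New Year crossing possible; they do not show that one occurred.

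Third, the effect is limited. TEAE status uses the start date, so a wrong AE end date changes no TEAE count. Safety is descriptive, and every event remains in the listings. The 3.6 points apply only if the subject has no other event counted at that level. For a medication begun well before the study, an end in January 2017 is possible; the rule is wrong only for one still in use after first dose.

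None of this removes the implausible dates or the concomitant-medication error, for which no second definition exists.

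**Conclusion.** The point holds as a minor defect. For a subject whose participation spans 31 December, the missing-month rules can place a start about 11 months after follow-up (nearer 12 in Cohort 1 when month and day are both missing) and an end before the first dose. The AE then fails the SAP 9.1 window but still counts under SAP 6.1.7 and Protocol 9.3. An on-treatment medication falls out of the concomitant table. AE end dates can become implausible, even earlier than their own start, without altering TEAE counts.

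The size is at most one subject per affected record, up to 3.6 points in a Cohort 2 arm of 28. This rests on a literal reading of SAP 6.1.8 and on an assumed first-dose date. Whether any subject was affected cannot be determined from the documents.

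**What to change.** In SAP 6.1.8, replace the missing-month rules with bounded ones:

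- **Start:** the earliest date compatible with the recorded parts that is on or after the first dose. If every compatible date precedes the first dose, keep it as pre-dose (prior). Without this clause the rule is undefined for, say, a medication recorded only as 2012.
- **End:** the latest compatible date not after the last date on study. If every compatible date is later, keep it as after the study.

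Separately, reconcile SAP 6.1.7 and 9.1 so that one TEAE window applies.

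In the worked example the starts become 01-Jan-2018 (Day 21) and 05-Jan-2018 (Day 25), treatment-emergent under all three definitions. The ends become 31-Dec-2017 and 20-Dec-2017. The three control starts do not change.

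The cost is a few sentences and a small change to the date-imputation code. The downside is that a medication stopped at an unknown time in the old year will count as concomitant for a subject dosed before that year's end, even if it stopped before dosing. That is the conservative direction.

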Study Procedure	Screen	Baseline	Week 1	Week 2	Week 3	Week 4	Week 4	Week 5
Weeks	-6	0	1	2	3	4		
Vehicle Application in Clinic (subject training) ^f			X ^f		X ^f			
Drug/Vehicle Application in Clinic ^g		X ^g		X ^g		X ^g		
ARQ-151 cream/Vehicle application at home		X	X	X ^h	X	X ^h		
Dispense study medication		X	X	X	X			
Weigh study medication		X	X	X	X	X		
Dispense/Review Diary		X	X	X	X	X	X ⁱ	
Adverse events assessments		X	X	X	X	X		
Concomitant medications	X	X	X	X	X	X		
Optional Skin biopsy ^j						X		
Telephone follow up ^j								X

^a Limited physical examination: skin, lungs, and heart only

^b Target Plaque Severity Score: Sum of erythema, induration, and scaling each scored 0-4 (maximum score = 12). Target plaque area = Longest diameter (cm) x Widest perpendicular diameter (cm). Up to three target plaques will be chosen, each at least 9 cm². The target plaques must each have a TPSS ≥ 4 . Subjects must have at least one target plaque.

^c Photography will be at selected investigational sites. Photography will be optional and confined to the target lesions. All efforts will be made to de-identify the subjects.

^d A urine pregnancy test will be administered to all females of child-bearing potential. A negative result is required for continued participation in the study, and results must be available prior to dispensing of study drug at each visit.

**STUDY EVENTS FLOW CHART: COHORT 2; 28 DAY APPLICATION TO 0.5 – 5% BSA;
DOUBLE BLIND, PLACEBO CONTROLLED (Continued)**

- e PK draws on day 1: 1, 2, 4 and 6 hours (\pm 10 minutes for 1, 2, 4 and 6 hour collections); day 14: pre-dose (trough) and 1-hour (\pm 10 minutes) post-dose; and day 28: pre-dose (trough), 1, 2, 4, 6 (\pm 10 minutes for 1, 2, 4 and 6 hour collections); and 24 hours (\pm 1 hour) post-dose for analysis. PKs will be collected from at least 45 volunteer subjects; PK collections will continue until PKs have been collected from 15 subjects in each treatment group.
- f Vehicle application training post baseline will be conducted as needed on Visits 3 (week 1) and 5 (week 3).
- g Drug or vehicle will be applied in clinic.
- h Visits 4 (week 2) and 6 (week 4) only: ARQ-151 cream or vehicle application will be done at home in the morning of Days 13 and 27 and in the morning at the clinic on PK collection Days 1, 14 and 28. ARQ-151 cream or vehicle will not be applied in the evening of Days 13 and 27.

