8.11.3 Treatment Compliance

Study medication tubes will be weighed at each follow-up clinic visit. Additionally, subjects will complete a daily diary recording the date and time of each dose applied, any missed doses, and a comment section should the subjects have a comment, e.g., record potential AEs. Site personnel will review the diaries and use the information to question the subject regarding compliance and AEs and then record appropriate information in source documents and complete Case Report Forms (CRFs). If a subject misses a dose, they should be instructed to return to the per protocol study medication administration schedule.

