- Change from baseline = value at current time point – value at baseline.
- Percent change from baseline = (change from baseline / baseline) * 100.
- TEAE = any AE with an onset date/time after first dose of study drug in each cohort.

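### A Cohort 2 AE in the hour of the first dose with its onset minute missing can never be treatment-emergent under SAP 6.1.7, and the SAP and protocol define TEAE in three different ways

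*SAP*

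**What the plan says.** Three places define a treatment-emergent AE, and each does so differently.

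- SAP 6.1.7: "TEAE = any AE with an onset date/time after first dose of study drug in each cohort". This works at date/time level and is strict.
- SAP 9.1: "start date during or after administration of the first dose of study drug", through the telephone follow-up. For an AE on the first-dose date, "if the time of onset is missing, the AE will be assumed to be treatment emergent".
- Protocol 9.3: "events with onset dates on or after the start of study drug or with missing onset dates". This works at date level only.

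SAP 6.1.8 sets out how incomplete times are filled in. Its rules tied to the dose time are limited to Cohort 1. For example, on the first-dose date, if "only hour is missing the hour assigned is 12 or the hour of first dose, whichever is later"; a missing minute is handled in the same way using 30, and a wholly missing time is set to the time of first dose. Cohort 2 gets fixed values instead: "If a Cohort 2 time is missing, set to 12:00; if time is incomplete, set to 12 (hour) or 00 (minute").

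SAP section 10, which lists changes from the protocol's planned analysis, does not mention the TEAE definition.

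**The concern.** A fixed value that ignores the dose time, combined with a strict rule that onset must follow the dose, pushes some first-day events to the wrong side of the line. The events most exposed are those that start soon after the first application, because these fall in the dose hour. For a topical product they are also events of particular interest.

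TEAE status decides entry to the overall, maximum-severity, treatment-related and discontinuation tables. Protocol 8.1.2 describes this as the first study of the cream in humans, safety is a primary objective, and Protocol 9.3 rests the safety assessment mainly on TEAE frequency. If the sections disagree, the tables depend on which one the programmer followed.

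**Working it through.** The plan gives no figure to reproduce, so the check applies its rules as written.

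**Inputs.** The TEAE definitions are those in SAP 6.1.7, SAP 9.1 and Protocol 9.3, and the time rules are in SAP 6.1.8. Protocol 8.16.1.4 has AE onset date and time noted. Protocol 8.11.3 has the subject's diary "recording the date and time of each dose applied".

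**1. Minute missing, onset in the dose hour.** Let the dose be at H:m, with m from 0 to 59.

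- Cohort 2 sets the onset to H:00. It is a TEAE under 6.1.7 only if 0 > m, which never happens: 0 of 60 dose minutes. Reading the rule as at or after (0 ≥ m) recovers only m = 0: 1 of 60.
- There are 60 × 59 / 2 = 1,770 same-hour minute pairs in which the true onset follows the dose. Under 6.1.7 none is counted.
- The Cohort 1 rule sets the minute to max(30, m). This exceeds m for m = 0 to 29, so 30 of 60 under strict after, and 60 of 60 under at or after.
- Example: dose 10:15, onset 10:-- becomes 10:00 and is not a TEAE.
- A missing minute in a later hour still gives a TEAE, so this loss is confined to the dose hour.

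**2. Hour missing, true onset after the dose.** Assumptions: lags of 1 to 240 minutes and every dose minute equally likely. The recorded minute is k, and Cohort 2 sets the onset to 12:k.

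- Dose before noon: 12:k is always later, so 0% are lost.
- Dose at 12:m: the event is lost when k ≤ m. The 240 lags cover each k four times, so the share lost is (m + 1)/60. Averaged over m this is (1 + 2 + … + 60)/(60 × 60) = 1,830/3,600 = 50.8%.
- Dose from 13:00: 12:k is always earlier, so 100% are lost.
- Under the Cohort 1 rule the loss is 0% before noon and 50.8% from noon on. Example: dose 14:30, onset --:10 becomes 14:10.

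**3. Time wholly missing.** Cohort 2 uses 12:00. For a dose at or after 12:00, even a post-dose event fails 6.1.7. For a dose between 08:00 and 11:59, a pre-dose event is counted for all 240 dose minutes. In Cohort 1 the onset is set equal to the dose time, which is not after it.

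**4. The definitions side by side, Cohort 2, first-dose date.**

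| Recorded onset | SAP 6.1.7 with 6.1.8 | SAP 9.1 | Protocol 9.3 |
|---|---|---|---|
| Dose hour, minute missing | Never a TEAE | TEAE if read by date, or if incomplete counts as missing; not stated | TEAE |
| Hour missing | Depends on dose clock time | Same uncertainty | TEAE |
| Time wholly missing | TEAE only if dose is before 12:00 | TEAE | TEAE |

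**5. How far steps 2 and 3 could reach.** The Cohort 2 flow chart (Protocol section 6, footnote h) places application "in the morning at the clinic on PK collection Days 1, 14 and 28". PK sampling covers at least 45 subjects, so at most 84 − 45 = 39 (46%) fall outside it. No document shows an afternoon first dose. Step 1 does not depend on the dose hour.

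**The case against.** The strongest reply is that SAP 9.1 is the operative section for AE analysis. Read at date level, it counts the 10:15 example and agrees with Protocol 9.3. It sends the reader to 6.1.8 only for missing and partial dates, not times. On that reading the exclusion arises only if 6.1.7 is taken alone. This reading is reasonable, but the SAP does not establish it. Section 9.1 names only a missing onset time, while 6.1.8 treats missing and incomplete times separately, and nothing says that 9.1 overrides 6.1.7. If 9.1 does govern, 6.1.7 is wrong as written.

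Other points stand in part:

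- The missing-hour losses need a first dose at or after noon and a minute recorded without an hour. They are hypothetical.
- Counting a pre-dose event of unknown time is not a reason to change the rule, because the remedy below does the same.
- It is unclear whether Cohort 2 first-dose time reaches the database. The planned Drug Application listing covers Cohort 1 only, while SAP 7.4 promises drug application listings for each cohort. Without that time, 6.1.7 could not be applied at all, whereas the rule proposed below would default to counting the event.
- The impact is small: no inferential safety test is planned, all AEs are listed, and dermal response scores are tabulated separately. Those scores do not, however, cover non-local events.

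**Conclusion.** The concern holds. Under SAP 6.1.7 with the Cohort 2 time rule, an AE in the dose hour on the first-dose date with its minute missing is excluded in every case (0 of 60 dose minutes). This follows from the rules alone and needs no assumption about dose time or lag. Wholly missing times and missing hours can be misclassified in either direction, depending on the clock time of the dose. The 50.8% and 100% figures apply only to doses from noon onward, under the assumed lags. The Cohort 1 convention is not a safe model either, since it fails the strict definition for wholly missing times and can place a missing hour before an afternoon dose. The number of events affected is unknown and probably confined to a few on the first day. The conflict should still be removed, because it can drop early reactions from the TEAE tables or make those tables depend on the section followed.

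**What to change.** Put one definition in SAP 6.1.7 and 9.1: onset at or after the first dose of study drug in that cohort. For both cohorts, add that an AE on the first-dose date with a missing or partial onset time is treatment-emergent unless the recorded part of the time shows that it began before the dose. State that neither the fixed 12:00/00 values nor the Cohort 1 time imputation is used to decide TEAE status. Record the difference from Protocol 9.3 in SAP section 10.

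Changing only the strict inequality is not enough, as it recovers 1 of 60 dose minutes under the :00 rule. The cost is a few sentences, using dose and onset times the protocol already asks for; the SAP team should confirm that Cohort 2 first-dose time is in the database. The downside is a slightly higher TEAE count, because some true pre-dose events with unknown times will be included.
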